## 2.4.2 Secondary Endpoints

- Recurrent hernias (functional hernias) requiring surgical intervention
- True recurrence at 24 months
- Evidence of Eventration/Hernia Recurrence (Radiographic)
- Fluid collection (Seroma, Hematoma)
- Surgical Site Infections
- Systemic Infections
- Enterocutaneous Fistula
- Dehiscence
- Implant failure requiring partial or total removal
- Patient satisfaction (using the SF-36 questionnaire) at Baseline, 3 months, 6 months, 12, and 24 months.
- Days to discharge
- Pain measured using the Visual Analog Scale for discomfort at Baseline, 3 months, 6 months, 12 months, and 24 months.
- Patient contentment with the cosmetic results at 12 months, 24 months and/or at the time of study withdrawal except for patients who have been withdrawn due to recurrence.

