## 3.1 Sample Size

Patients will be randomized at a 1:1 ratio. A total of 120 patients, 60 Strattice and 60 Fortiva patients will be enrolled. This sample size will give the study a 95% significance level and 80% power and shall provide preliminary data and benchmark evidence for direct comparison of two post-market biologic mesh materials when used as reinforcement in large abdominal hernias. The analysis also contemplates a 15 to 20% dropout rate for the primary outcome.

Power analysis and sample size determination is based on Log-rank test for equality of recurrence rates over time during the study between groups. The hazard rates of recurrence are key quantities. Often the hazard rates are very hard to obtain. However, based on the mathematical relationships of hazard function and recurrence function, we can derive the hazard rate from either of two related quantities which are

often reported in literature –(1) the proportion of recurrence-free during the study period or (2) median recurrence-free time, from Kaplan-Meier product limit survival curve.

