#### 3.2 Statistical Plan

Given the 1:1 randomized nature of the clinical trial and to preserve the inherent characteristics of the randomization, analysis by intention-to-treat (ITT) is chosen. This type of analysis compares the study groups in terms of the treatment to which they were randomly allocated, irrespective of the treatment they actually received or other trial outcomes. Regardless of protocol deviations and participant compliance or withdrawal, analysis is performed according to the assigned treatment group. This type of analysis will also help to demonstrate if there is superiority of one mesh over the other.

If there is no superiority of one mesh over the other, analysis will be performed using the same outcomes to assess if there is equivalence between both meshes. This will demonstrate that there is no clinically significant difference between the two treatment arms.

For statistical analysis, these outcomes can be classified into two measurement scales- continuous and categorical. For continuous outcome, mean and standard deviation, median and range for each group will be calculated. ANOVA will be used to compare the difference in the means among the two groups when data are reasonably normally distributed. Otherwise, non-parametric ANOVA will be used. For categorical data, proportion will be obtained for each outcome, along with 95% CI derived from exact method. Difference in the proportions among the four groups will be compared using Fisher's exact test.

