# 5.3.3 Subject Withdrawal and Discontinuation

Subjects may withdraw consent to participate at any time during the study for any reason. The Investigator may also withdraw a subject from the study if the subject:

- i. Is in deviation of the protocol
- ii. Experiences a serious or intolerable AE
- iii. Develops symptoms or conditions listed in the exclusion criteria during the course of the study
- iv. Requests an early discontinuation for any reason

Information regarding all withdrawn or lost-to-follow-up subjects will be documented on the Study Disposition Form. Patients will either complete all the necessary study requirements or their participation in the study may prematurely end for one or more reasons. Patients will be considered "Withdrawn" due to: death, a concurrent illness that prohibits continued participation, the Investigator elects to withdraw the participant due to reasons listed above or because he/she voluntarily withdraws consent at any time during the study for any reason. Such withdrawals shall be documented on the Study Disposition Form. All available information concerning death or concurrent illness should be documented and evaluated for adverse event reporting. If the participant withdraws his/her consent, he/she should be asked (when possible and without coercion) the reason for the decision and notified that data already collected will continue to be

part of the study as per the consent form he/she signed at the time of enrollment. No further study procedures will take place after the participant requests to be withdrawn from the study.

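### VAS pain and SF-36 are scored at four post-operative times, but section 3.2 names only a two-group ANOVA or rank equivalent, so later-visit differences may be biased by dropout and are slightly less precise

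*Combined protocol and SAP*

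**What the plan says.** Section 2.4.2 (Secondary Endpoints) lists "Pain measured using the Visual Analog Scale for discomfort at Baseline, 3 months, 6 months, 12 months, and 24 months" and "Patient satisfaction (using the SF-36 questionnaire) at Baseline, 3 months, 6 months, 12, and 24 months". The schedule in 6.10 agrees: one baseline score and four post-operative scores for each instrument.

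For continuous outcomes, section 3.2 (Statistical Plan) gives one method: "ANOVA will be used to compare the difference in the means among the two groups when data are reasonably normally distributed". The fallback is one sentence: "Otherwise, non-parametric ANOVA will be used". It names no visit of interest, visit term or covariance structure, and gives no rule for missing scores. On the analysis set, 3.2 says: "Regardless of protocol deviations and participant compliance or withdrawal, analysis is performed according to the assigned treatment group".

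Three further passages bear on which scores will be missing:
- Section 3.1: "The analysis also contemplates a 15 to 20% dropout rate for the primary outcome".
- Section 5.3.3 lets the investigator withdraw a patient who "Experiences a serious or intolerable AE" or who develops a condition on the exclusion list. It adds: "No further study procedures will take place after the participant requests to be withdrawn from the study". Data obtained before withdrawal are kept.
- Section 2.3 and the visit descriptions in section VI end scheduled follow-up once a true recurrence is diagnosed. Only re-operation data are collected after that.

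**The concern.** A two-group comparison of means at 12 or 24 months can use only patients who have a score at that time. A patient who left at 7 months adds nothing to the 12-month test, although the 3- and 6-month scores are in the database and help to predict the missing one. The result describes the patients who stayed. The intention-to-treat wording fixes the arm in which a patient is counted, but does not say how a patient without a score is to be counted.

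Patients in more pain or worse health may well leave more often. If one arm really is worse, it then sheds more of its bad scores and the observed difference shrinks. Section 3.2 also provides that, if superiority is not shown, equivalence is assessed on the same outcomes. If that covers these scores, shrinkage towards zero would favour a finding of equivalence.

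**Working it through.** The documents state no sample size, power, SD or effect for VAS or SF-36, so there is no planned figure to reproduce.

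**Inputs from the documents:** 60 per arm (3.1); post-operative scores at 3, 6, 12 and 24 months (2.4.2, 6.10); dropout of 15-20%, stated for the primary outcome only (3.1).

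**Assumptions:** SD 1; true difference 0.5 SD or zero; between-visit correlation 0.5-0.7; two-sided 5% test (3.1 does not give sidedness); odds of leaving that do or do not rise with the previous score.

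**Step 1: patients available to a visit-wise test.** SE = SD × √(2/n), and the detectable difference at 80% power is (1.960 + 0.842) × SE.

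| n per arm | SE | Detectable difference | Power for 0.5 SD |
|---|---|---|---|
| 60 | √(2/60) = 0.183 | 0.51 SD | 78% |
| 60 × 0.85 = 51 | √(2/51) = 0.198 | 0.55 SD | 71% |
| 60 × 0.80 = 48 | √(2/48) = 0.204 | 0.57 SD | 69% |

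A model that uses earlier scores recovers only part of this loss.

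**Step 2: dropout unrelated to scores.** Simulated trials (visits at 3, 6 and 12 months, post-operative scores only, about 17-23% missing at 12 months) compared the 12-month ANOVA difference with a maximum-likelihood repeated-measures estimate. Neither was biased. The model's SE was 3-6% smaller, and its power was about 2-5 points higher with normal scores.

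**Step 3: score-related dropout, same mechanism in both arms, true difference 0.5 SD.** The ranges pool two sets of simulations, with 1500 and 4000 trials per scenario.

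| Odds of leaving per SD of previous score | ANOVA estimate | ANOVA power | Model estimate | Model power |
|---|---|---|---|---|
| ×2.0 (log-odds slope 0.7) | 0.47-0.49 | 64-68% | 0.49-0.51 | 71-76% |
| ×2.7 (log-odds slope 1.0) | 0.44-0.47 | 59-65% | 0.49-0.51 | 70-74% |

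Example (correlation 0.6, slope 1.0):
- ANOVA: mean 0.444, SD 0.203. Attenuation is (0.500 − 0.444)/0.500 = 11%, and power is Φ(0.444/0.203 − 1.96) = 59%.
- Model: mean 0.491, SD 0.198. Power is Φ(0.491/0.198 − 1.96) = 70%.

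A further run with 20-22% missing gave ANOVA estimates of 0.46-0.48 against 0.50 for the model. Attenuation across the runs is about 3-11%.

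**Step 4: no true difference.**
- Same mechanism in both arms: the effects cancel, and ANOVA bias is −0.01 to +0.01 SD.
- Mechanism differing by arm (leaving depends on scores in one arm only, or many more leave in one arm, about 9% against 28%): ANOVA bias is −0.08 to −0.14 SD, and the model stays close to zero.

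**Step 5: skewed scores.** The model still removed the bias, but its precision gain disappeared when dropout was score-related.

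**Step 6: is 15-20% the right missing rate?** A recurrence counts as an observed primary outcome, yet it ends the questionnaires, so more scores than primary outcomes may be missing. As an illustration, take the 18-50% background recurrence range in 2.2 and assume independence from other dropout. Then 60 × 0.85 × 0.82 ≈ 42 down to 60 × 0.80 × 0.50 = 24 per arm remain, with a detectable difference of about 0.61-0.81 SD for a plain two-group test. Section 2.2 does not offer that range as a forecast for this trial.

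**The case against.** The strongest reply is that the plan is silent rather than wrong. Section 3.2 does not say that leavers are excluded, and it does not set out one test per visit. That is simply what the named method does when applied to observed scores. This stands, and it limits the wording of the point. A reader might infer that the plan discards the earlier scores of everyone who leaves. It does not: 5.3.3 keeps them, and in visit-wise tests they count at the earlier visits. They are unused only in the later comparison.

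The second reply concerns size. Even the 0.444 example is off by 0.056/0.203 = 0.28 of a standard error, so a nominal 95% interval would still cover about 94% of the time. The dropout odds and the 0.5 SD difference have no source in the documents. That also stands: the bias is conditional and modest.

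Third, withdrawal for an adverse event is at the investigator's discretion. The compulsory stop is at recurrence, and a repeated-measures model does not resolve that by itself. It assumes that scores after recurrence can be predicted from those before it. This must be stated and tested.

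Fourth, using the baseline score would gain more precision than using earlier post-operative scores: the SE is multiplied by √(1 − r²), which is 0.87 at r = 0.5 and 0.71 at r = 0.7. That is true, but it is a separate choice. The gains in Steps 2 and 3 use no baseline.

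Finally, a normal-likelihood model gives up the rank fallback for bounded and possibly skewed scores. That is a fair cost, and the fix keeps the rank test as support.

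**Conclusion.** The point holds as a conditional one. For scores measured repeatedly, the only named method ignores information already collected, and it needs dropout to be unrelated to the scores. A likelihood-based model needs only the weaker assumption that missingness is explained by the observed scores.

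Under the assumed scenarios, a true 0.5 SD difference is attenuated by about 3-11% when the dropout mechanism is the same in both arms. A spurious difference of about 0.1 SD appears when the mechanism differs by arm. Harmless dropout costs about 2-5 power points with normal scores.

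A reader might go further and conclude that the later-visit differences are biased as a matter of course. The documents do not support that. Bias needs leaving to be related to the scores, together with a difference between arms in scores or in mechanism, and nothing in the documents establishes either. Nor is the trial's main conclusion at risk: these are secondary endpoints, and the primary recurrence comparison is unaffected. The change is a worthwhile, inexpensive improvement.

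**What to change.** In section 3.2, make these changes for VAS and SF-36:
- Use a likelihood-based repeated-measures model with arm, visit and arm-by-visit terms and an unstructured covariance. Include all available scores of randomised patients, by assigned arm.
- Report the arm difference with a 95% CI at each visit, with 12 months as the main contrast.
- State that scores after recurrence are not collected and are treated as missing at random in this model.
- Add a sensitivity analysis for that assumption, for example shifting the unobserved scores after recurrence or withdrawal by a stepped amount in each arm.
- Keep the visit-wise rank test as a supportive analysis if scores are clearly non-normal.
- Leave ANOVA or the rank test in place for outcomes measured once, such as days to discharge.

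The cost is SAP wording and slightly more programming, with no new patients, visits or data. The downsides are a missing-at-random assumption, though weaker than the one ANOVA needs, and a normal likelihood for bounded scores. If only post-operative scores enter the model, a patient with none still contributes nothing, and the text should say so.

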#### 2.4 Study Endpoints

## 2.4.1 Primary Endpoints

The primary objective of this study is to compare the incidence of true hernia recurrence (true defect in the implant repair in which intra-abdominal contents are protruding through the defect) at or before 1 year between the Fortiva™ Porcine Dermis group compared with Strattice™ Reconstructive Tissue Matrix group.

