# 5.2 Eligibility Criteria

#### 5.2.1 Inclusion Criteria

- 18 years of age or greater
- Have a BMI < or equal to 40

- Have a pre-operative estimated hernia defect of 200 cm2 OR multiple hernia defects whose combined area is ≥ an estimated 200 cm2. Patients whose defects do NOT meet or exceed 200 cm2 intra-operatively will be withdrawn from the study and will be considered an intra-operative screen failure
- Have no contraindications to the test material (s)
- Have a life expectancy greater than 1 year in the opinion of the Investigator
- Able to provide informed consent
- Able and willing to return for scheduled study visits over 2 years post-operatively (following research related surgery)

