#### 6.2.1 Data to be collected intra-operatively:

- 1. Documentation of indication for surgery (i.e. incisional hernia, re-do hernia repair, etc.)
- 2. Documentation of size and location of hernia defect
- 3. Operative start and finish times
- 4. Determine if the subject has an active infection and if so, subject is withdrawn from study and is considered a "screen failure"

- 5. Determine if subject's abdomen is unable to be closed primarily and if so, subject is withdrawn from study and is considered a "screen failure"
- Operative procedure details including all research related information (detail in OR Notes)
   \*\*\*Make sure all details are documented in the OR note (i.e. sutures used and where, number of drains inserted and where, overlap, etc. when possible)
- 7. Type and dimensions of graft used
- 8. Product and serial numbers of graft used
- 9. Fixation procedures
- 10. Concomitant procedures
- 11. Photographic documentation of graft placement prior to closure, post-closure
- 12. Complications during surgery (note any and all complications including uncontrolled bleeding, subject becoming unstable, error with mesh placement, etc.) and record these events as AE/SAE's as applicable
- 13. Medications given during surgery

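### The 1-year recurrence comparison is unadjusted and randomisation unstratified, so a small, assumption-dependent gain in precision and some protection against chance imbalance are forgone

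*Combined protocol and SAP*

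**What the plan says.** Section 2.4.1 compares the incidence of true recurrence "at or before 1 year between the Fortiva" group and the Strattice group, which is a yes/no outcome. For categorical outcomes, section 3.2 gives proportions with exact 95% intervals and then states: "Difference in the proportions among the four groups will be compared using Fisher's exact test". (The trial has two arms; the reference to four groups is a separate slip.) Section 3.1 rests the sample size on another test: "Power analysis and sample size determination is based on Log-rank test for equality of recurrence rates over time during the study between groups". That test is also described without covariates or strata. Section III contains no regression model and no stratified test. Section 5.3.2 describes 1:1 tables and sealed envelopes and names no stratification factor.

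The relevant patient features can be obtained from planned data:

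- **Defect size.** Eligibility in 5.2.1 requires that patients "Have a pre-operative estimated hernia defect of 200 cm2", or multiple defects whose combined area reaches that figure. Size and location are recorded again at surgery (6.2.1, item 2).
- **Previous repair.** Surgical history is taken at Visit 1 (6.1). Section 6.2.1, item 1, asks for "Documentation of indication for surgery (i.e. incisional hernia, re-do hernia repair, etc".

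Section 1.1 lists repeated earlier repair among the features that make a hernia complex. It does not link it to recurrence.

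**The concern.** Defect size and previous repair are fixed before the implant is placed and plausibly predict recurrence. With roughly 50 to 60 patients per arm, the arms can differ noticeably on either by chance. Neither the allocation nor the analysis responds to that. Any such difference then feeds into the observed recurrence difference, and precision that planned data could supply is not used.

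Timing matters too. The surgeon knows the allocation (5.3.2), and the sponsor sees unblinded summaries about every 12 months (3.4). If an imbalance is noticed later, an adjustment chosen then would be open to challenge as post hoc.

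**Working it through.** **1. The plan's own figure.** Section 3.1 says: "A total of 120 patients, 60 Strattice and 60 Fortiva patients will be enrolled" and "This sample size will give the study a 95% significance level and 80% power". This cannot be reproduced, because no hazard rate, hazard ratio or recurrence proportion is given. Back-solving for 80% power at two-sided 0.05 with 60 per arm gives 50% vs 25.5% or 30% vs 9.8% (two proportions), or 50% vs 26.1% (log-rank, hazard ratio 0.44).

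**2. Evaluable patients.** Section 3.1 also says: "The analysis also contemplates a 15 to 20% dropout rate for the primary outcome". Then 60 × 0.85 = 51 and 60 × 0.80 = 48 per arm.

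**3. Chance imbalance.** Assume half the patients have had a previous repair. With X₁ and X₂ independent Binomial(n, 0.5), the probability that |X₁ − X₂|/n is at least d is:

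| n per arm | d = 10 points | d = 15 points | d = 20 points |
|---|---|---|---|
| 60 | 31.5% | 12.0% | 3.5% |
| 51 | 27.6% | 13.7% | 3.7% |
| 48 | 35.8% | 12.5% | 5.2% |

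At 60 per arm, the probability of strictly more than 10 points is 23.5%. For defect size, the standardised difference has standard error √(2/n), which is 0.183 at 60 and 0.204 at 48. A difference of 0.2 or more then occurs in 27% to 33% of trials, and 0.3 or more in 10% to 14%.

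**4. What an imbalance does.** Take 30% recurrence overall. Solve 0.5p₀ + 0.5·OR·p₀/(1 − p₀ + OR·p₀) = 0.30 for p₀, let p₁ be the risk with a previous repair, and multiply p₁ − p₀ by 0.15 for a 15-point imbalance:

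| OR for previous repair | p₀ | p₁ | Shift in risk difference |
|---|---|---|---|
| 1.5 | 25.8% | 34.2% | 1.3 points |
| 2 | 22.8% | 37.2% | 2.2 points |
| 3 | 18.9% | 41.1% | 3.3 points |

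**5. Precision.** Simulation of 3,000 trials per cell, 50 per arm, 20% vs 42–45% recurrence, size as N(0,1) and re-do as Bernoulli(0.5):

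| OR per SD of size, OR for re-do | SE unadjusted | SE adjusted | Change |
|---|---|---|---|
| 1.35, 1.5 | 0.0902 | 0.0897 | −0.6% |
| 1.65, 2.0 | 0.0896 | 0.0879 | −1.9% |
| 2.0, 2.7 | 0.0908 | 0.0851 | −6.3% |

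With neither factor prognostic, a second simulation (4,000 trials per scenario, 51 and 60 per arm) gave variance ratios of 1.015 to 1.025. Since √1.015 = 1.007 and √1.025 = 1.012, the standard error rises by about 1%.

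**6. Power.** From the second simulation, 51 per arm, 50% vs 25%:

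| OR per SD of size, OR for previous repair | Fisher | Chi-square | Adjusted logistic |
|---|---|---|---|
| 1, 1 | 69.3% | 76.2% | 75.0% |
| 1.5, 1.5 | 68.8% | 75.8% | 76.1% |
| 1.5, 2 | 70.5% | 77.4% | 77.7% |
| 2, 3 | 69.3% | 76.6% | 81.1% |

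Moving from Fisher to an unadjusted chi-square is worth about 7 points in every row. Adjustment then adds −1.2 to +4.5 points. With no true difference (30% in both arms, 60 per arm), Fisher rejected in 2.7% to 4.1% of trials.

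In the 50-per-arm simulation, an adjusted z-test without size control appeared to raise power from 75.9% to 77.7%, from 72.2% to 76.2% and from 64.4% to 72.2%. The standard errors alone explain less. Power is Φ(z − 1.96), with z scaled by the ratio of the standard errors:

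- 2.663 × 0.0902/0.0897 gives 76.4%.
- 2.549 × 0.0896/0.0879 gives 73.8%.
- 2.329 × 0.0908/0.0851 gives 70.0%.

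The adjusted test's rejection rate under the null was 5.0% to 5.9%, against 4.9% to 5.4% unadjusted. With the size held at 5%, the change against chi-square at 50 per arm was about −1 point (no or weak prognostic strength), +1 (middle) and +4 (strong).

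**7. Events.** Section 2.2 cites recurrence of 18% to 50%. With 2 × 51 = 102 evaluable patients, that is 0.18 × 102 ≈ 18 to 0.50 × 102 = 51 events, enough for one or two covariates.

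**The case against.** The strongest reply is that nothing here is an error. Under 1:1 randomisation the unadjusted intention-to-treat comparison is valid, and its test and intervals already allow for chance imbalance. This stands. A reader might infer from the missing adjustment that the recurrence comparison is biased or its error rate inflated. The documents do not support that: there is no bias on average, and Fisher's test is conservative.

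A reader might also infer a power gain of 2, 4 or 8 points from the z-test comparison in step 6. That is too much, because part of it reflects the adjusted test's slightly raised type I error. The documents give no prognostic strength for either factor, and the eligibility floor near 200 cm² narrows the range of defect size, which may weaken it as a predictor.

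A third tempting reading is that both covariates are already clean baseline fields. They are not. Neither Visit 1 (6.1) nor the schedule (6.10) has a dedicated item for pre-operative defect area. The size listed for recording is intra-operative, and re-do repair is only an example under indication for surgery.

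Finally, the log-rank sizing, the Fisher analysis and the unstated handling of dropouts leave the primary analysis unsettled. Those are separate and arguably larger problems. They do not remove this one, and section 3.2 has to be rewritten for them anyway.

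**Conclusion.** The point holds as a minor, low-cost improvement. The plan neither stratifies nor adjusts, although defect size and previous repair can be obtained from planned data. The loss is a standard error about 0 to 6% larger than necessary over the assumed odds ratios, and no protection against realised imbalance; a 15-point imbalance in previous repair would shift the risk difference by about 1 to 3 points. If neither factor predicts recurrence, nothing is lost and adjustment would cost about 1% in standard error. The size-controlled change in power against chi-square is −1 to +4 points.

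These figures assume prognostic strength, 50% prevalence of previous repair, a normally distributed size measure, and the recurrence rates stated in each step. None of these is a design input in the documents. It would be wrong to credit adjustment with the whole advantage over the planned test, since most of that comes from leaving Fisher's test.

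**What to change.** Before unblinded data are reviewed, pre-specify in section 3.2:

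- **Main estimate.** The 1-year recurrence risk difference with 95% CI, standardised from a logistic model with arm, log defect area and any previous ventral hernia repair (yes/no).
- **Data sources.** For defect area, use the pre-operative estimate made for eligibility and name the source record. It is preferable to the intra-operative measurement, which may be taken when the surgeon knows the allocation. For previous repair, use the Visit 1 surgical history. Confirm that both are captured for every patient.
- **P-value.** Obtain it by re-randomisation that follows the actual allocation tables, so that the size stays at 5%.
- **Supportive analysis.** Keep the unadjusted comparison. The rule for patients without 1-year status, which is needed in any case, should apply to both analyses.

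The cost is SAP wording, modest programming and a check of two source fields. The downside is reliance on one working model with few events, so use no more than these two covariates, and accept a slight loss of precision if neither is prognostic. The interval and the re-randomisation p-value may disagree in borderline cases, so state in advance which governs.

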## 2.2 Surgical Technique:

The major source of structural integrity and strength of the abdominal wall is provided by the musculofascial layer. The main paired abdominal muscles include the external oblique muscles, internal oblique muscles, transversus abdominis muscles, and rectus abdominis muscles and their respective aponeuroses, which are interdigitated with each other, and provide core strength and protection to the abdominal wall viscera. The integrity of the abdominal wall is essential not only to protect the visceral structures but also to stabilize the trunk and to aid trunk movement and posture.

Complex abdominal wall defects, including incisional abdominal wall hernias, are a challenging surgical problem. Incisional hernias occur in 10 to 23 percent of open abdominal laparotomies, with recurrence rates reported between 18 and 50 percent (deHartog, et al, 2008; Lowe et al. 2000^15, Sailes et al, 2011 .). The Component Separation Technique (CST), a type of rectus abdominis muscle advancement flap, was first used to reconstitute the linea alba, reduce abdominal wall tension, and provide a dynamic abdominal wall in patients with large abdominal wall defects (Ramirez et al. 1990^17). CST allows reconstruction of a large defect without requiring a free distant transposition flap (de Vries et al. 2003). The advantages of CST are that it restores structural support of the abdominal wall, provides stable vascularized soft tissue coverage, and optimizes aesthetic appearance of complex abdominal wall defects and giant midline abdominal wall hernias (Shestak et al. 2000). In this protocol, abdominal wall mobilization will be conducted in an attempt to bring the fascia together. If this is unable to be completed with circumferential undermining, component separation will be performed bilaterally.

Patients will then be randomized 1:1 to one of two treatment assignments:

- Fortiva™ Porcine Dermis retrorectus/underlay
- Strattice™ Reconstructive Tissue Matrix retrorectus/underlay

Procedure: After the abdominal wall mobilization is completed, and the Investigator determines that the primary fascial closure can be obtained, the assigned implant will be prepared according to the manufacturer's instructions and will be immediately available for the surgery.

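### Section 3.2 compares all proportions with Fisher's exact test, which is valid but conservative at 60 per arm; Boschloo's exact test would recover some power at the cost of a wording change

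*Combined protocol and SAP*

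**What the plan says.** Section 3.2 sorts outcomes into continuous and categorical. For categorical data it plans an exact 95% interval for each proportion and then one test: "Difference in the proportions among the four groups will be compared using Fisher's exact test". It names no other test for proportions and no interval for the difference between arms. The reference to four groups is a slip, since the trial has two arms.

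The primary endpoint in Section 2.4.1 is the incidence of true recurrence at or before 1 year. That is a binary outcome, so as written it falls under this rule. So do binary secondary outcomes in Section 2.4.2 such as infection, fistula, dehiscence and implant removal.

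Section 3.1 sets the size: "A total of 120 patients, 60 Strattice and 60 Fortiva patients will be enrolled", with the statement that "This sample size will give the study a 95% significance level and 80% power". It adds that "The analysis also contemplates a 15 to 20% dropout rate for the primary outcome". The power statement belongs to a different test: "Power analysis and sample size determination is based on Log-rank test for equality of recurrence rates over time". No hazard rate, event rate or effect size is given; the text says only "Often the hazard rates are very hard to obtain" and describes how a rate could be derived.

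**The concern.** Fisher's test conditions on the total number of events. With 60 or fewer patients per arm the set of attainable p-values is coarse, and the true false-positive rate falls well short of the nominal 5%. The unused part costs power. An unconditional exact test can use more of the 5% and still guarantee it. At stake is modest sensitivity for recurrence analysed as a proportion, and more for uncommon complications.

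**Working it through.** **Inputs from the documents.** 60 per arm, 1:1; 5% level (Section 3.1); dropout of 15 to 20%, which leaves 60 × 0.85 = 51 or 60 × 0.80 = 48 per arm if 60 is the gross number. Section 2.2 gives background recurrence, "with recurrence rates reported between 18 and 50 percent", but does not declare it as a design input.

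**Assumptions.** Two-sided testing (not stated), and all event rates below.

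**The plan's own 80%.** It can be neither reproduced nor refuted, because no effect is stated. One can only solve for the effect that it would need. Use power = Φ(√(D/4)·|ln HR| − 1.96), with D = 60(p1 + p2) and HR = ln(1 − p2)/ln(1 − p1):
- 24% vs 7.2%: D = 18.72, HR = 0.272, so Φ(2.163 × 1.301 − 1.96) = Φ(0.85) = 80%.
- 50% vs 26.1%: D = 45.66, HR = 0.436, so Φ(3.379 × 0.829 − 1.96) = Φ(0.84) = 80%.

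These are log-rank figures and say nothing about Fisher's test.

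**Exact enumeration.** For x and y events among n per arm:
- Fisher's p is the sum of all hypergeometric probabilities C(n,i)·C(n,m−i)/C(2n,m), m = x + y, that do not exceed the observed one.
- Size(π) = ΣΣ b(x; n, π)·b(y; n, π) over tables with p ≤ 0.05. Power is the same sum with π1 and π2.
- Boschloo's test rejects when Fisher's p ≤ c, where c is the largest value that keeps the maximum of Size(π) over π at or below 0.05.

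**Cut-offs.** c = 0.0665 at 60 per arm and 0.0693 at 50, each with maximum size 4.9%. At 51 and 48 per arm c also exceeds 0.05 and maximum size stays below 5%. Because c exceeds 0.05, every table that Fisher's test rejects is also rejected by Boschloo's.

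**True size of Fisher's test at 60 per arm:**

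| Common rate | 1% | 2% | 5% | 10% | 20% | 30% | 40% | 50% |
|---|---|---|---|---|---|---|---|---|
| Size | 0.0% | 0.1% | 1.1% | 2.2% | 2.8% | 3.1% | 3.2% | 3.5% |

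Over rates of 18 to 50% it is 2.8 to 3.5% at 60 per arm, 2.7 to 3.7% at 51 and 2.6 to 3.2% at 48. Boschloo's size at 60 per arm is 3.4 to 4.9% for rates of 10 to 50%.

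**Power, Fisher to Boschloo (%), gain in points from unrounded values:**

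| Rates | 60 per arm | 51 per arm | 48 per arm |
|---|---|---|---|
| 2 vs 10% | 27.7 to 39.5 (11.8) | 19.9 to 31.3 (11.5) | 17.3 to 28.4 (11.1) |
| 10 vs 30% | 73.0 to 77.4 (4.4) | 65.3 to 70.7 (5.4) | 61.3 to 67.2 (5.8) |
| 20 vs 40% | 60.0 to 64.6 (4.5) | 52.7 to 57.8 (5.1) | 49.0 to 53.8 (4.7) |
| 25 vs 50% | 76.0 to 81.0 (5.0) | 69.0 to 74.6 (5.6) | 64.3 to 71.0 (6.7) |
| 30 vs 50% | 54.2 to 61.0 (6.8) | 48.0 to 53.4 (5.5) | 43.1 to 51.0 (7.8) |

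**Spread.** Across all pairs with a lower rate of 5 to 50% and Fisher power of 50 to 85%, the gain is 1.9 to 6.9 points (median 4.4) at 60 per arm, 0.5 to 7.3 (median 3.9) at 51 and 2.6 to 7.8 (median 5.5) at 48. Where Fisher's power is already 80% at 60 per arm, the gain is 2.8 to 4.4 points.

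**The case against.** The strongest reply is that Fisher's test is prespecified, familiar and controls type I error, and that Section 3.1 promises 80% power for a log-rank test, so no promised power is missed. All of that stands. It is why this is an efficiency point and not a defect.

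Three stronger readings are tempting, and the documents do not support them.

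- *That every categorical outcome is tested at 2 to 3% and loses 4 to 7 points.* At 60 per arm, size lies between 2 and 3% only for common rates of about 9 to 26%. It is lower for rare complications and higher over much of the quoted recurrence range. The gain also varies beyond 4 to 7 points, and the documents give no rates that would fix it.
- *That a less sensitive test leads to false claims of equivalence.* Section 3.2 says "If there is no superiority of one mesh over the other, analysis will be performed using the same outcomes to assess if there is equivalence". Entering that assessment is not declaring equivalence. With 10 vs 30% at 60 per arm, 100 − 73.0 = 27.0% of trials would enter it under Fisher and 100 − 77.4 = 22.6% under Boschloo. The weakness there is that no margin or method is given, and changing the superiority test supplies neither.
- *That any modern interval can accompany the new test without cost.* Miettinen-Nurminen is an asymptotic score interval without guaranteed coverage, and it can disagree with Boschloo. Take 13/60 vs 5/60. The difference is 0.1333 and the pooled rate 0.15, so z = 0.1333/√(0.15 × 0.85 × 2/60) × √(119/120) = 2.04, and the interval excludes zero. Fisher's p is 0.071, above the 0.0665 cut-off, so Boschloo does not reject.

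It is also fair to say that the larger issue here is the mismatch between a log-rank sample size and an analysis section with no time-to-event method. Resolving that could take the primary endpoint away from Fisher's test altogether; the binary secondary outcomes would remain.

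**Conclusion.** The point holds as a free improvement. For two-arm comparisons of proportions at 48 to 60 per arm, Boschloo's test is never less powerful than Fisher's and still guarantees the 5% level. The usual benefit is a few points of power at mid-range rates, with more for uncommon events, though power for those stays low under either test (39.5% at best for 2 vs 10%). The size of the gain rests on assumed event rates, two-sided testing and the number evaluable. It should be quoted as a range.

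**What to change.** In Section 3.2, prespecify Boschloo's unconditional exact test at two-sided 5% for two-arm comparisons of proportions. Report the risk difference with a 95% confidence interval obtained by inverting an unconditional exact test. If a score interval such as Miettinen-Nurminen is preferred, label it approximate and state that the Boschloo p-value governs. In the same edit, change four groups to two groups in Section 3.2 and the 95% significance level to 5% in Section 3.1.

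The cost is wording only: no extra patients, visits or data, and standard software has the test. Make the change before anyone responsible for the analysis sees outcomes by arm, since Section 3.4 provides for unblinded sponsor summaries about every 12 months. The equivalence margin and the log-rank/Fisher mismatch need their own corrections.
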